9.4.2 Safety Endpoints

Safety and tolerability will be assessed by clinical review of all relevant parameters including AEs, physical examinations, and vital signs.

The primary safety endpoints for RSV Season 1 are:

- Number of participants with solicited injection-site AEs (redness/erythema, swelling, and pain/tenderness) from Days 1 through 5 after each dose.

- Number of participants with fever (defined as maximum rectal temperature $\geq 102.2^{\circ}\text{F}$ [$\geq 39.0^{\circ}\text{C}$] or axillary temperature $\geq 101.7^{\circ}\text{F}$ [$\geq 38.7^{\circ}\text{C}$]) from Days 1 through 5 after each dose.
- Number of participants with solicited systemic AEs (irritability, drowsiness, and appetite lost) from Days 1 through 5 after each dose.
- Number of participants with anaphylaxis/hypersensitivity AESI from Days 1 through 28 after Dose 1 and Days 1 through 14 after Dose 2.
- Number of participants with rash AESI from Days 1 through 28 after Dose 1 and Days 1 through 14 after Dose 2.
- Number of participants with any nonserious AEs from Days 1 through 28 after Dose 1 and 14 days after each subsequent dose.
- Number of participants with SAEs through the duration of participation in RSV Season 1.

The secondary safety endpoints for RSV Season 2 are:

- Number of participants with solicited injection-site AEs (redness/erythema, swelling, and pain/tenderness) from Days 1 through 5 postdose.
- Number of participants with fever (defined as maximum rectal temperature $\geq 102.2^{\circ}\text{F}$ [$\geq 39.0^{\circ}\text{C}$] or axillary temperature $\geq 101.7^{\circ}\text{F}$ [$\geq 38.7^{\circ}\text{C}$]) from Days 1 through 5 postdose.
- Number of participants with solicited systemic AEs (irritability, drowsiness and appetite lost) from Days 1 through 5 postdose.
- Number of participants with anaphylaxis/hypersensitivity AESI from Days 1 through 42 postdose.
- Number of participants with rash AESI from Days 1 through 42 postdose.
- Number of participants with any nonserious AEs from Days 1 through 42 postdose.
- Number of participants with SAEs from Days 1 through 180 postdose.

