3 HYPOTHESES, OBJECTIVES, AND ENDPOINTS

This is an estimation study without hypotheses. The following objectives will be evaluated in the study population. The RSV Season 1 42-day safety follow-up period consists of safety data collected from Day 1 post Dose 1 through 14 days post Dose 2.

Primary Objectives	Primary Endpoints

 RSV Season 1: To evaluate the safety and tolerability of MK-1654 compared to palivizumab in RSV Season 1 as assessed by the proportion of participants experiencing AEs. 	
 Solicited injection-site AEs from Days 1 through 5 after each dose Solicited daily body temperature, with fever defined as rectal temperature $\geq 102.2^{\circ}\text{F}$ ($\geq 39.0^{\circ}\text{C}$) or axillary temperature $\geq 101.7^{\circ}\text{F}$ ($\geq 38.7^{\circ}\text{C}$) from Days 1 through 5 after each dose Solicited systemic AEs from Days 1 through 5 after each dose Anaphylaxis/hypersensitivity AESI from Days 1 through 42 post Dose 1 Rash AESI from Days 1 through 42 post Dose 1 Nonserious AEs from Days 1 through 42 post Dose 1 and 14 days after each subsequent dose SAEs through the duration of participation in RSV Season 1
Secondary Objectives	Secondary Endpoints

 RSV Season 1: To estimate the efficacy of MK-1654 compared to palivizumab as assessed by the incidence of RSV-associated MALRI (outpatient and inpatient) from Days 1 through 150 post Dose 1 in RSV Season 1. 	
 RSV-associated MALRI (outpatient and inpatient), defined as the following seen in an outpatient or inpatient clinical setting: 
 Cough or difficulty breathing; AND 
 1 or more of the following: wheezing, chest wall in-drawing/retractions, rales/crackles, hypoxemia, tachypnea, dehydration due to respiratory symptoms; AND 
 RSV-positive RT-PCR NP sample

 • RSV Season 1: To estimate the incidence of RSV-associated hospitalizations from Days 1 through 150 post Dose 1 in RSV Season 1 in the MK-1654 and palivizumab groups. 	
 • RSV-associated hospitalization, defined as the following: 
 ▪ Hospital admission for respiratory illness; AND 
 ▪ RSV-positive RT-PCR NP sample

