9.1 Statistical Analysis Plan Summary

Key elements of the statistical analysis plan are summarized below; the comprehensive plan is provided in Section 9.2 through Section 9.12.

Study Design Overview	A Phase 3, Multicenter, Randomized, Partially Blinded, Palivizumab-Controlled Study to Evaluate the Safety, Efficacy, and Pharmacokinetics of MK-1654 in Infants and Children at Increased Risk for Severe RSV Disease
Treatment Assignment	A total of 1000 participants will be randomized in a 1:1 ratio to the MK-1654 or palivizumab groups on Day 1 (double-blind) in RSV Season 1. All participants who continue into RSV Season 2 will receive 1 dose of MK-1654.
Analysis Populations	Efficacy: Full Analysis Set (FAS) and Per-Protocol Efficacy (PPE) Safety: All Participants as Treated (APaT) Pharmacokinetic: Per-Protocol (PP)
Primary Endpoint(s)	Safety 
 Number of participants with solicited injection-site AEs from Days 1 through 5 after each dose in RSV Season 1. Number of participants with fever as measured by solicited daily body temperatures from Days 1 through 5 after each dose in RSV Season 1. Number of participants with solicited systemic AEs from Days 1 through 5 after each dose in RSV Season 1. Number of participants with anaphylaxis/hypersensitivity AESI from Days 1 through 28 after Dose 1 and Days 1 through 14 after Dose 2 in RSV Season 1. Number of participants with rash AESI from Days 1 through 28 after Dose 1 and Days 1 through 14 after Dose 2 in RSV Season 1. Number of participants with nonserious AEs from Days 1 through 28 after Dose 1 and 14 days after each subsequent dose in RSV Season 1. Number of participants with SAEs through the duration of study participation in RSV Season 1.

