In addition to individual events that occur in 1% or more participants in any treatment group, the broad AE categories consisting of the proportion of participants with any AE, a drug-related AE, an SAE, an AE which is both drug-related and serious, discontinuation due to an AE, solicited injection-site AE, solicited systemic AE, solicited AE of fever measured by body temperatures, anaphylaxis/hypersensitivity AESI, rash AESI, and nonserious AE will be considered Tier 2 endpoints.

Tier 3 Events

Safety endpoints that are not Tier 1 or 2 events are considered Tier 3 events. Only point estimates by treatment group are provided for Tier 3 safety parameters.

Table 7 Analysis Strategy for Safety Parameters

Safety Tier	Safety Endpoint	95% CI for Comparison of MK-1654 and Palivizumab	Descriptive Statistics
Tier 2	Any AE ^a	X	X
	Any SAE	X	X
	Any Drug-Related AE	X	X
	Any Serious and Drug-Related AE	X	X
	Discontinuation Due to AE	X	X
	Solicited Injection-Site AEs Days 1-5 Postdose	X	X
	Solicited Daily Body Temperature Days 1-5 Postdose	X	X
	Solicited Systemic AEs Days 1-5 Postdose	X	X
	Anaphylaxis/hypersensitivity AESI Days 1-42 Post Dose 1 in RSV Season 1 ^b and 42 Days Postdose in RSV Season 2	X	X
	Rash AESI Days 1-42 Post Dose 1 in RSV Season 1 ^b and 42 Days Postdose in RSV Season 2	X	X
	Nonserious AEs Days 1-42 Post Dose 1 in RSV Season 1 ^b and 42 Days Postdose in RSV Season 2	X	X
	AEs by SOC (incidence $\geq 1\%$ of participants in one of the treatment groups)	X	X
Tier 3	AEs by SOC (incidence $< 1\%$ of participants in all of the treatment groups)		X
AE=adverse event; AESI=adverse event of special interest; CI=confidence interval; RSV=respiratory syncytial virus; SAE=serious adverse event; SOC=System Organ Class; X=results will be provided. ^a Indicates broad AE category of the number of participants reporting any AE. ^b Days 1-42 post Dose 1 in RSV Season 1 consists of safety data collected from Day 1 post Dose 1 through 14 days post Dose 2.			

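### Sections 9.1 and 9.4.2 split the Season 1 primary AESI window into two blocks, contrary to the continuous window of Sections 1.1, 3 and Table 7, whose end is undefined when Dose 2 is not given

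*Combined protocol and SAP*

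**What the plan says.** For AESI there are two definitions of the Season 1 primary window.

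- **Continuous.** The endpoint row in Section 3 reads "Anaphylaxis/hypersensitivity AESI from Days 1 through 42 post Dose 1". The preamble to Section 3, repeated in Section 1.1, defines the 42-day period as "safety data collected from Day 1 post Dose 1 through 14 days post Dose 2". Footnote b of Table 7 (Section 9.6.2) says that the period "consists of safety data collected from Day 1 post Dose 1 through 14 days post Dose 2".
- **Two blocks.** Section 9.4.2 has "Number of participants with anaphylaxis/hypersensitivity AESI from Days 1 through 28 after Dose 1 and Days 1 through 14 after Dose 2". Section 9.1 has "anaphylaxis/hypersensitivity AESI from Days 1 through 28 after Dose 1 and Days 1 through 14 after Dose 2 in RSV Season 1". Both sections word the rash AESI endpoint the same way.

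For nonserious AEs there are three versions.

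- Section 3: "Nonserious AEs from Days 1 through 42 post Dose 1 and 14 days after each subsequent dose".
- Section 9.4.2: "Number of participants with any nonserious AEs from Days 1 through 28 after Dose 1 and 14 days after each subsequent dose", with the same window in Section 9.1.
- Table 7: the 42-day window only, with no follow-up after later doses.

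Collection is continuous. Section 8.4.1 requires reporting from randomization to 14 days after Dose 2, and Section 8.4.8 sets the same end for AESI.

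**The concern.** These are primary endpoints, and safety is the primary objective. The two definitions do not always count the same events. The two-block version can omit events that sites recorded while dosing within the permitted window. It also stops at Day 28 for infants who receive only Dose 1, although Section 9.5.2 keeps them in the APaT population and Section 7.1 keeps them under follow-up.

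Section 4.2.3 justifies the Day 28 placebo injection by the need for an unbiased 42-day safety assessment after Dose 1. An endpoint rule that can drop part of those 42 days works against that purpose. If the conflict stays, the choice of which count to report could be made after data have accrued.

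**Working it through.** **Inputs**

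- Dose 2 is given 28 to 32 days after Dose 1 (Section 1.2, schema footnote a; Section 1.3.1.1, Day 28 with a +4 window).
- The day of the previous dose counts as Day 1 when visit windows are calculated (Section 4.1).
- There are 500 infants per arm (Section 2.3).

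**The plan's own figure.** 28 + 14 = 42, so the two blocks add up to the stated 42 days.

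**Late Dose 2.** Let d be the study day of Dose 2, with the dose day as Day 1 of its own 14-day block. Section 9.4.2 counts Days 1 to 28 and Days d to d + 13. The continuous window counts Days 1 to d + 13. The days not counted by 9.4.2 are Day 29 to Day d − 1.

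| Dose 2 on study day | Counted by 9.4.2 | Continuous window | Not counted by 9.4.2 |
|---|---|---|---|
| 28 | 1–28, 28–41 | 1–41 | none |
| 29 | 1–28, 29–42 | 1–42 | none |
| 30 | 1–28, 30–43 | 1–43 | Day 29 (1/43 = 2.3%) |
| 31 | 1–28, 31–44 | 1–44 | Days 29–30 (2/44 = 4.5%) |
| 32 | 1–28, 32–45 | 1–45 | Days 29–31 (3/45 = 6.7%) |
| 33 (elapsed-day reading of the dosing window) | 1–28, 33–46 | 1–46 | Days 29–32 (4/46 = 8.7%) |

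The blocks form an exact Days 1–42 only when Dose 2 falls on Day 29. If the blocks themselves are also read as elapsed days, the first runs to study Day 29, and the gap is at most 2 days for a Day 32 dose and 3 for Day 33. If Dose 2 were spread evenly over Days 28 to 32 (an assumption), the mean gap would be (0 + 0 + 1 + 2 + 3)/5 = 1.2 days.

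**No Dose 2.** Section 9.4.2 counts Days 1–28 only. Against 42 days it loses 42 − 28 = 14 days, or 14/42 = 33% for that infant. The continuous definition has no end date, because its end is tied to Dose 2. The same holds for reporting under 8.4.1 and 8.4.8.

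The documents give no rate of missed Dose 2. For an assumed proportion m, the person-days lost per arm are 500 × m × 14, out of 500 × 42 = 21,000.

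| Assumed m | Infants per arm | Person-days lost | Share of window |
|---|---|---|---|
| 1% | 5 | 70 | 0.3% |
| 5% | 25 | 350 | 1.7% |
| 10% | 50 | 700 | 3.3% |

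**With the continuous window throughout.** The gap is 0 days for every Dose 2 date, and the window ends on Days 41 to 45 for Dose 2 on Days 28 to 32. A stated end at Day 42 when Dose 2 is not given restores Days 29–42 for those infants.

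**The case against.** The best defence is that 28 + 14 in Section 9.4.2 is only a loose breakdown of the same 42 days. Table 7 sets the analysis strategy for the between-group intervals, and it uses the continuous window. Nothing is lost from the database when Dose 2 is late, because collection is continuous. An infant who stops study intervention stays on the visit schedule, which includes AE review at the Day 42 call. On Table 7, Section 9.6.2 limits the primary comparison to the first two doses, which may be why the nonserious AE row omits later follow-up.

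Most of this stands as a limit on the size of the problem. It does not remove the conflict: 9.4.2 is the section that defines the endpoints, its literal rule counts differently from Table 7, and no passage says which governs. The supplemental comparison in 9.6.2 covers all palivizumab doses and needs the follow-up that the Table 7 row leaves out.

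Some stronger readings are tempting but are not supported:

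- A reader might infer that AESI have three different windows. Section 3 and Table 7 footnote b agree; only nonserious AEs have three versions.
- A reader might infer that Section 3 cuts off at a fixed Day 42 and so loses events after a late Dose 2. Its preamble defines the 42-day period as running to 14 days after Dose 2.
- A reader might infer informative loss, since Section 7.1 allows stopping for an untoward effect. But each endpoint counts participants, so an infant with an AESI of that category by Day 28 is already counted. Bias would need a first event of the category in Days 29–42 in an infant without Dose 2, and the documents do not show that such infants are at higher risk.
- A reader might assume that AESI are rare, so that one or two events decide the result. No AESI rate is given, and the terms in Section 8.4.8.1 include wheezing and dyspnea in a trial planning at least 200 infants with CLD.

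**Conclusion.** The point holds as an inconsistency in a primary endpoint definition. Sections 9.1 and 9.4.2 conflict with Sections 1.1 and 3 and with Table 7, so Section 9 also contradicts itself. Taken literally, the two-block rule leaves up to 3 recorded days uncounted for an infant given Dose 2 on Day 32 (4 on the elapsed-day reading of the dosing window), and everything after Day 28 for an infant without Dose 2.

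The impact on the results is probably small. Both arms share the same blinded Dose 2 window, no hypothesis is tested, and SAEs are counted throughout Season 1 whichever definition applies. The 6.7% and 33% figures are worst cases for a single infant. The loss of 0.3% to 3.3% of window person-time per arm covers missed Dose 2 only and rests on an assumed 1% to 10% missing it. Nothing here shows bias between the arms. The reason to act is that the rule would leave out recorded events and is easy to correct.

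**What to change.** - In 9.1 and 9.4.2, replace the two-block wording for both AESI endpoints with the continuous window of Section 3 and Table 7: Day 1 through 14 days after Dose 2.
- State, wherever the window is defined, that it ends at Day 42 after Dose 1 when Dose 2 is not given. Put the same end point in 8.4.1 and 8.4.8.
- For nonserious AEs, use the continuous window in 9.1 and 9.4.2, keep the 14 days of follow-up after each subsequent dose, and add it to the Table 7 row. A single window for all primary AE endpoints would be wrong, because it would delete the follow-up after later palivizumab doses.

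The cost is low. The changes to Section 9 are wording only. The end date in 8.4.1 and 8.4.8 is a reporting rule for sites, so it needs amended protocol text and notice to sites, but no new visit: the Day 42 contact is already in Section 1.3.1.1.

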9.4.3 Pharmacokinetic, Pharmacodynamic, and Immunogenicity Endpoints

The secondary pharmacokinetic endpoints are:

- PK concentration of MK-1654 at Days 7, 150, and 240 after the dose of MK-1654 in RSV Season 1.
- PK concentration of MK-1654 at Days 7 and 150 after the dose of MK-1654 in RSV Season 2.

The tertiary immunogenicity endpoints are:

- Incidence and magnitude of ADA to MK-1654 on Day 1 (predose), Days 150 and 240 post Dose 1 in RSV Season 1, and Days 7 and 150 postdose in RSV Season 2.

The tertiary pharmacodynamic endpoints are:

- The titer of SNA to RSV A on Day 1 (predose) and Days 7, 150, and 240 post Dose 1 in RSV Season 1, and Days 7 and 150 postdose in RSV Season 2.

An additional tertiary endpoint is:

- RSV F gene sequence determined by deep sequencing in NP samples from infants infected with RSV in RSV Seasons 1 and 2.

9.5 Analysis Populations

9.5.1 Efficacy Analysis Populations

Full Analysis Set (FAS) Population

The FAS population will serve as the primary population for the estimation of efficacy and for the estimation of incidence of RSV-associated disease. The FAS population consists of all randomized participants who receive at least 1 dose of study treatment. Participants will be included in the treatment group corresponding to the study treatment they were randomized to for the analysis using the FAS population.

For an episode of respiratory infection to be considered for evaluation of an efficacy endpoint for the analysis in the FAS population, a PCR result from the study central laboratory must be available for an NP sample that is collected between 0 and 12 days after symptom onset and between 7 days before and 12 days after symptom worsening. A sensitivity analysis will be conducted, which will include PCR results from NP samples collected within the timeframe mentioned above but not tested at the study central laboratory.

Per-Protocol Efficacy (PPE) Population

The PPE population will serve as a supportive analysis population for the estimation of efficacy and incidence of RSV-associated disease. To be eligible for inclusion in the PPE population, study participants must satisfy the following criteria:

- Receive a complete regimen of the correct clinical material corresponding to the treatment group the participants were randomized into (ie, 1 dose of MK-1654 for participants randomized to the MK-1654 group and 3 to 5 doses of palivizumab within the protocol-specified windows for participants randomized to the palivizumab group based on the date of enrollment and the predefined RSV season end date at each site),
- Have at least 1 follow-up visit/contact for assessment of RSV disease,

- Do not undergo 1) ECMO or 2) surgical intervention for CHD requiring cardiopulmonary bypass during the efficacy follow-up period (Day 150 or Day 180), and
- At any time during dosing or efficacy follow-up, do not experience a protocol deviation that may interfere with the assessment of protection against RSV infection conferred by MK-1654.

The final determination on important protocol deviations, and thereby the composition of the PPE population, will be made prior to the final database lock and will be documented in a separate memo.

For an episode of respiratory infection to be considered for evaluation of an efficacy endpoint for the analysis in the PPE population, a PCR result from the study central laboratory must be available for an NP sample that is collected between 0 and 12 days after symptom onset and between 7 days before and 12 days after symptom worsening.

For both analysis populations, if a participant with symptoms of respiratory infection prior to dosing has an NP sample collected predose on RSV Season 1 Day 1 or any subsequent NP samples collected for this episode that are PCR positive for RSV, this episode will not be counted as a case toward the efficacy endpoints.

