
 Cough Difficulty breathing 	
 Wheezing Chest wall in-drawing/Retractions Rales/Crackles Hypoxemia (SpO₂ <95% on room air at sea level, <92% on room air at altitude ≥1800 m, or 5 percentage points or more below baseline level in children with CLD or CHD with chronic underlying hypoxemia)^a Tachypnea (RR ≥60 breaths per minute for <2 months of age; ≥50 breaths per minute for 2 to 12 months of age; or ≥40 breaths per minute for >12 to 24 months of age) Dehydration due to respiratory symptoms 	
 RSV-positive RT-PCR NP sample (collected within 12 days of symptom onset or worsening)
CHD=congenital heart disease; CLD=chronic lung disease; LRI=lower respiratory infection; MALRI=medically attended lower respiratory infection; NP=nasopharyngeal; RR=Respiratory rate; RSV=respiratory syncytial virus; RT-PCR=reverse transcriptase-polymerase chain reaction; SpO ₂ =oxygen saturation as measured by pulse oximetry. ^a For severe MALRI: Severe hypoxemia (SpO ₂ <90% on room air at sea level; <87% on room air at altitude ≥1800 m) or the need for high flow nasal cannula, oxygen mask, or mechanical ventilatory support.		

In addition, RSV-associated MALRI and hospitalization through 180 days postdose in RSV Seasons 1 and 2 and RSV-associated severe MALRI through 150 days postdose in RSV Season 1 are planned as tertiary endpoints. The burden of RSV-associated hospitalizations is described in Section 2.2, and a decrease in hospitalization rate represents a benefit to public health.

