8.2.2 Respiratory Infection Assessment

8.2.2.1 Requirements for Scheduling a Respiratory Infection Assessment

To identify potential cases of RSV-associated LRI, participants with any respiratory infection symptoms should be assessed at the site by the investigator or medically qualified designee. RSV-associated MALRI is defined in Section 4.2.1.1.

A respiratory infection assessment is required when:

- Respiratory infection symptoms are reported (see Section 8.2.1).
- New or worsening LRI signs/symptoms arise during an existing respiratory infection episode.
- The participant is seen in an outpatient or inpatient clinical setting for respiratory infection symptoms.

The respiratory infection assessment should be performed within 3 days of symptom onset or worsening.* If this is not possible or the visit for the assessment is missed, it can be performed within 12 days of symptom onset or worsening.*

***Note:** Symptom onset or worsening may refer to the symptom onset or worsening that led to the outpatient visit or hospital admission.

A respiratory infection assessment may occur during an unscheduled visit or at a scheduled study visit if that visit occurs within the time requirements noted above.

Every attempt should be made to assess the participant at the study site. If this is not possible, a home visit or visit to an alternate study site may be used, where available and when

permitted by local regulations and IRB/IEC. In the case of a home visit or visit to an alternate study site, all indicated study procedures should be performed, including NP sample collection for RT-PCR testing at the central laboratory.

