8.2.3 Nasopharyngeal Sample Collection for RT-PCR Testing for Respiratory Virus Identification

NP samples should be collected within the time requirements for the respiratory infection assessment in Section 8.2.2.1.

The swabs for collecting NP samples for RT-PCR testing are provided by the central laboratory. Sample collection, storage, and shipment instructions for the NP sample are provided in the laboratory manual.

All swabs collected for NP sampling by a qualified designee will be sent to the central laboratory for analysis. The analysis will determine the common viral cause(s) of LRI as well as the strain of RSV (ie, RSV A or B) if RSV is detected. Additional details are available in the laboratory manual.

An NP sample should be collected for RT-PCR testing for respiratory virus identification if any respiratory symptoms are observed during a respiratory infection assessment (see Section 8.2.2). If a participant requires collection of another sample(s) (at the same visit or any subsequent visits), the subsequent sample(s) should be taken from the same nostril as the first sample.

The following procedures should be followed for obtaining RT-PCR results for respiratory virus identification during a nonstudy visit to an outpatient clinic, Emergency Department,

urgent care center, or hospital visit (ie, other than during a scheduled or unscheduled visit to the study site), under each of the following circumstances:

1. Site staff can collect NP sample at a nonstudy visit

If a participant first visits an outpatient facility or hospital (ie, a nonstudy visit) and is confirmed to have respiratory symptoms, the study staff should make every effort to obtain an NP sample using the study-supplied swab, as permitted, and the site should send this sample to the central laboratory for analysis.

2. Site staff cannot collect NP sample at a nonstudy visit

If an NP sample using the study-supplied swab cannot be collected by site staff during an outpatient visit or hospitalization, the sample should be collected using the study-supplied swab as soon as possible postvisit or postdischarge. The medical records (if available) should also be obtained from the outpatient facility or hospital.

Note: Collection of the NP sample using the study-supplied swab during either of the above circumstances should be within the time requirements in Section 8.2.2.1.

3. PCR results from a local laboratory

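### Section 9.5.1 requires one swab to fall in both the onset and the worsening window, while Table 1 and the site instructions accept either, so some on-time MALRI episodes are not counted as written

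*Combined protocol and SAP*

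**What the plan says.** **Counting rule.** Section 9.5.1 states, for the FAS (the primary efficacy population), that the sample must be "collected between 0 and 12 days after symptom onset and between 7 days before and 12 days after symptom worsening". The PPE paragraph repeats the condition, including the span "between 7 days before and 12 days after symptom worsening". The planned sensitivity analysis admits PCR results from other laboratories but keeps this timeframe.

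**Endpoint definition.** Table 1 in Section 4.2.1.1 asks for an "RSV-positive RT-PCR NP sample (collected within 12 days of symptom onset or worsening". Section 9.4.1 defines the first secondary endpoint by reference to Section 4.2.1.1, so the SAP itself takes in Table 1.

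**Site instructions.** Section 8.2.2.1 sets the target: "The respiratory infection assessment should be performed within 3 days of symptom onset or worsening". If that is missed, "it can be performed within 12 days of symptom onset or worsening". Section 8.2.3 applies the same timing to swabs: "NP samples should be collected within the time requirements for the respiratory infection assessment in Section 8.2.2.1". Section 8.2.2.2 calls for a swab at the first assessment of an episode, and another when lower-tract signs appear or worsen later in the same episode. Section 8.2.1.1 ends an episode only after 48 symptom-free hours and sets no maximum length.

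The limit of 7 days before worsening appears only in Section 9.5.1.

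**The concern.** The definition and the site instructions join the two dates with *or*; the counting rule joins them with *and*. An infant can meet the MALRI definition, be swabbed when the site was told to swab, test positive, and still not be a case. Missing data are not imputed (Table 6), so in the FAS that infant stays in the denominator as a non-case.

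The rule covers any efficacy endpoint, so it governs the MALRI comparison and the per-group hospitalization incidences alike. If the text is left as it is, someone must choose a reading when the analysis is programmed. Under Sections 6.3.3 and 9.2 the sponsor knows each participant's assignment from the Day 60 visit, so that choice of case definition would be made with treatment known.

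**Working it through.** **1. Reproducing the plan's precision figures.** Table 8 assumes 500 per group and 10% attrition, so n = 450. The row used has incidences of 0.045 (MK-1654) and 0.060 (palivizumab).
- Exact Poisson limits, χ²(0.025; 2c)/2n and χ²(0.975; 2c+2)/2n, give 0.0276 to 0.0693 and 0.0395 to 0.0873. Table 8 prints (0.028, 0.069) and (0.040, 0.087).
- Closed-form SE(log RR) = √[(1−p₁)/(n·p₁) + (1−p₂)/(n·p₂)] = √(0.955/20.25 + 0.940/27) = 0.286. With RR = 0.045/0.060 = 0.75, efficacy is 25.0% (−31.5, 57.2). Simulation gives mean limits of (−37.7, 55.9), and Table 8 prints (−35.9, 56.5).

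The plan's figures reproduce. Expected cases are 20.25 + 27 = 47.25.

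**2. Comparing the windows.** Set onset at Day 0, worsening at Day w and the swab at Day s (days since symptom onset, not study days). Within 12 days is read as 0 to 12 days after.
- Table 1: 0 ≤ s ≤ 12 *or* 0 ≤ s−w ≤ 12.
- Section 9.5.1: 0 ≤ s ≤ 12 *and* −7 ≤ s−w ≤ 12, which reduces to max(0, w−7) ≤ s ≤ 12.

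| Worsening day w | Swab days meeting both windows | Failing: swabs 0–3 days after worsening | Failing: swabs 0–12 days after worsening | Failing: first swab on Days 0–3 |
|---|---|---|---|---|
| 3 | 0–12 | 0 of 4 | 3 of 13 | 0 of 4 |
| 7 | 0–12 | 0 of 4 | 7 of 13 | 0 of 4 |
| 9 | 2–12 | 0 of 4 | 9 of 13 | 2 of 4 |
| 10 | 3–12 | 1 of 4 | 10 of 13 | 3 of 4 |
| 11 | 4–12 | 2 of 4 | 11 of 13 | 4 of 4 |
| 13 | 6–12 | 4 of 4 | 13 of 13 | 4 of 4 |
| 20 | none | 4 of 4 | 13 of 13 | 4 of 4 |

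The columns describe single swabs. An episode is lost only if none of its swabs qualifies.

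**3. An episode that is lost.** Onset is Day 0, worsening Day 11, repeat swab Day 13. The repeat swab is 2 days after worsening, inside the 3-day target and Table 1, but 13 days after onset, so it fails Section 9.5.1. A first swab on Days 0–3 is 8 to 11 days before worsening and also fails. Table 1 counts the episode; Section 9.5.1 does not.

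**4. An episode that is kept.** With worsening on Day 10 and a repeat swab on Day 13, a first swab on Day 3 is exactly 7 days before worsening and meets both windows.

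**5. Size, under an assumed loss.** The documents give no frequency. Take a loss of 5% to 10%, equal in both groups.
- Cases lost: 47.25 × 0.05 = 2.4 to 47.25 × 0.10 = 4.7.
- Interval width scales roughly as 1/√cases: 1/√0.95 = 1.026 and 1/√0.90 = 1.054. The closed-form SE rises from 0.286 to 0.294 and 0.303, or 2.7% and 5.7%.
- Ratio: 0.75 before and after.
- Incidences: 4.5% falls to 4.28% or 4.05%, and 6.0% to 5.7% or 5.4%.

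**The case against.** The strongest reply is that *and* merely lists two windows, each used where its date exists. The literal reading leaves an episode without worsening unable to satisfy the second condition, which the sponsor can hardly have meant. That is plausible, but Section 9.5.1 does not say so and its grammar puts both conditions on one sample. Section 8.2.2.1 also notes that "Symptom onset or worsening may refer to the symptom onset or worsening that led to the outpatient visit or hospital admission". That note is permissive, and the SAP does not carry it over. If alternatives were intended, the text still needs correcting.

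A reader might infer more than the documents support:
- *That late lower-tract disease is removed in general.* Section 4.2.1.1 describes several days of mild upper-tract signs before lower-tract involvement. A swab within 3 days of worsening passes for any worsening up to Day 9 (9 + 3 = 12), and any one qualifying sample is enough.
- *That the hospitalization definition is contradicted too.* It contains no swab window. Section 9.5.1 narrows the hospitalization count but contradicts nothing in its definition.
- *That losses are far larger because non-worsening episodes all fail.* This rests on the least plausible reading. What stands is that these episodes have no stated workable rule.
- *That the efficacy estimate is biased.* Equal loss leaves the ratio unchanged. A 10% loss in one group only would move 25.0% to 32.5% (1 − 0.75 × 0.9) or 16.7% (1 − 0.75/0.9). Open-label follow-up makes unequal loss possible, but nothing in the documents shows it.

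**Conclusion.** The conflict is in the current text, affects both efficacy populations, and is not relieved by the planned sensitivity analysis. As written, the rule miscounts some MALRI episodes that meet Table 1. Those at risk worsen from about Day 10 after onset, or are swabbed late under the 12-day fallback, and have no other sample in both windows.

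The size is unknown. On the assumed 5% to 10% equal loss, the cost is modest: about 2 to 5 of some 47 expected cases, an interval about 3% to 5% wider, an unchanged ratio, and group incidences understated in proportion. The understatement also matters for hospitalization, which is reported as an incidence per group, where equal losses do not cancel.

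Efficacy is a secondary objective of an estimation study without hypotheses. This is a should-fix: the wording conflict is certain, the number of cases lost is not.

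**What to change.** Before any further review of unblinded data, replace the joint condition in both the FAS and PPE paragraphs of Section 9.5.1 with one explicit rule, and put the same wording in Table 1:
- **Episode without worsening:** a sample taken 0 to 12 days after symptom onset.
- **Episode with worsening:** a sample taken from 7 days before to 12 days after the worsening that meets the LRI criteria, regardless of days since onset.

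Report the plain Table 1 reading (within 12 days of onset or worsening) as a sensitivity analysis beside the local-laboratory one.

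Changing *and* to *or* is not enough. Any swab in the first 12 days would then count however much later the infant worsened: a Day 1 positive would serve for worsening on Day 30 of one long episode. The 7-day limit, which plausibly ties the RSV result to the lower-tract illness, would no longer constrain early swabs. *Or* would also admit a Day 20 swab before worsening on Day 27, which current Table 1 does not; the rule above admits that swab too, but openly and with Table 1 amended to match.

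The cost is a text change in two SAP paragraphs and one table, plus one extra analysis. No new samples are needed, and the worsening date is already presupposed by Section 9.5.1.
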